7.2.2.5.1 Management and documenting of immediate hypersensitivity reactions

Immediate hypersensitivity reactions are known and anticipated reactions occurring with monoclonal antibodies. Standard precautions must be taken for the subjects regarding routine IV infusion complications. Appropriate medical management according to local guidelines and standard operating procedures should be implemented if an immediate hypersensitivity reaction is suspected (e.g., appropriate medical treatment, reducing or stopping the infusion rate, etc.).

Clinical Study Code No.: CLI-10067AA1-01	Version No.: 6.0
EUDRACT No.: 2022-001079-15	Date: 06 July 2023

Immediate hypersensitivity reactions [15] should be considered in all cases where any symptoms or signs related to the acute/hypersensitivity reactions occur during or within 24 hours from infusion. All efforts should be made to accurately document symptoms, signs, and vital signs to allow accurate characterisation of the reaction.

In case of occurrence of symptoms and signs indicative of the immediate hypersensitivity reactions the Investigator is asked to duly record (but not limited to) the following data:

- Exact time when the reaction started and the duration of the reaction
- Oxygen saturation, respiratory rate, blood pressure, and 12-lead ECG
- Signs or symptoms including, but not limited to:
 - cutaneous and SC involvement: generalised erythema, urticaria, periorbital oedema, angioedema, pruritis, or flushing
 - signs of cardiovascular compromise: cyanosis, arrhythmia, collapse, diaphoresis, or incontinence
 - nervous system involvement: dizziness, confusion, or loss of consciousness
 - gastrointestinal tract involvement: abdominal pain, vomiting, or nausea
 - respiratory involvement: dyspnoea, wheezing-bronchospasm, stridor, chest, or throat tightness.

If any other symptoms/signs, these should be specified. In addition, additional blood samples will be collected as described in [Section 7.2.2.5](#).

The severity grade of the immediate hypersensitivity reactions should be assessed by the Investigator, considering the following grading system [18]:

1. Mild (skin and SC tissues only)
 - a. Generalised erythema, urticaria, periorbital oedema, or angioedema.
2. Moderate (features suggesting respiratory, cardiovascular, or gastrointestinal tract involvement)
 - a. Dyspnoea, stridor, wheeze, bronchospasm, chest, or throat tightness
 - b. Abdominal pain, nausea, or vomiting

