 - c. Dizziness (presyncope), or diaphoresis.
3. Severe (hypoxia, hypotension, or neurological compromise)
 - a. Cyanosis or hypoxemia (oxygen saturation \leq 92%)
 - b. Hypotension (systolic blood pressure $<$ 90 mmHg)
 - c. Confusion, collapse, loss of consciousness, or incontinence.

Clinical Study Code No.: CLI-10067AA1-01	Version No.: 6.0
EUDRACT No.: 2022-001079-15	Date: 06 July 2023

Characterisation of the immediate hypersensitivity reactions will be performed at the end of study after all clinical and biochemical data are available and analysed by Safety Advisory Committee.

Anaphylactic reactions, defined as IgE mediated, are not expected to occur during the first administration. However, when an anaphylactic reaction is suspected, CHF10067 should be discontinued immediately and appropriate therapy as per standard of care including epinephrine, diphenhydramine, corticosteroids, oxygen, and volume expansion should be administered.

Clinical criteria to diagnose anaphylaxis are summarised below [19]:

Anaphylaxis is highly likely when any 1 of the following 3 criteria is fulfilled:

1. Acute onset of illness (minutes to several hours) with involvement of the skin, mucosal tissue, or both (e.g., generalised urticaria, pruritis, flushing, or angioedema)

AND at least 1 of the following

- a. Respiratory compromise (e.g., Dyspnoea, wheeze-bronchospasm, stridor, chest tightness, or hypoxemia [oxygen saturation $\leq 92\%$])
- b. Hypotension (blood pressure < 90 mmHg) or associated symptoms of end-organ dysfunction (e.g., collapse, syncope, or incontinence).

2. **Two or more** of the following that occur after exposure (minutes to several hours):

- a. Involvement of the skin, mucosal tissue, or both (e.g., generalised urticaria, pruritis, flushing, or angioedema)
- b. Respiratory compromise (e.g., dyspnoea, wheeze-bronchospasm, stridor, chest tightness, or hypoxemia [oxygen saturation $\leq 92\%$])
- c. Hypotension (blood pressure < 90 mmHg) or drop in blood pressure ($> 30\%$ of subject's baseline) or associated symptoms of end-organ dysfunction (e.g., collapse, syncope, or incontinence)
- d. Persistent gastrointestinal symptoms (e.g., abdominal pain, nausea, or vomiting).

3. Reduced blood pressure after exposure to a known allergen for that subject (minutes to several hours):

- a. Systolic blood pressure of < 90 mmHg

OR

- b. Drop in systolic blood pressure $> 30\%$ decrease from that subject's baseline.

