10.3 Intensity of Adverse Event

For the classification of AEs severity (except for immediate hypersensitivity reactions severity, see below), the Common Terminology Criteria for Adverse Events (CTCAE) [23] will be used:

- Grade 1 Mild; asymptomatic or mild symptoms; clinical or diagnostic observations only; intervention not indicated.
- Grade 2 Moderate; minimal, local, or noninvasive intervention indicated; limiting age-appropriate instrumental Activities of Daily Living (ADL)*.
- Grade 3 Severe or medically significant but not immediately life-threatening; hospitalization or prolongation of hospitalization indicated; disabling; limiting self-care Activities of Daily Living**.
- Grade 4 Life-threatening consequences; urgent intervention indicated.
- Grade 5 Death related to AE.

*Instrumental ADL refer to preparing meals, shopping for groceries or clothes, using the telephone, managing money, etc.

**Self-care ADL refer to bathing, dressing and undressing, feeding self, using the toilet, taking medications, and not bedridden.

In order to guarantee objectivity and consistency in the evaluation of AEs (including classification of severity), the proposed guidance should be followed in alignment with best medical practice.

Laboratory abnormalities and other clinical assessments (e.g., 12-lead ECG) will be reported as AEs if judged by the Investigator as being clinically significant.

In case of laboratory evaluations or other clinical assessments (e.g., 12 -lead ECG) not listed in the CTCAE grading table, the AE severity will be judged by the Investigator based on the local ranges.

Taking into consideration the disease examined in the current study, it should be acknowledged that the guidance may not always be applied. Therefore, although the guidance should be followed, whenever possible, in order to ensure an accurate and objective evaluation of the AEs, the final decision on the severity classification remains the responsibility of the Investigator.

For the specific classification of severity and management of immediate hypersensitivity reactions, refer to [Section 7.2.2.5.1](#).

Clinical Study Code No.: CLI-10067AA1-01	Version No.: 6.0
EUDRACT No.: 2022-001079-15	Date: 06 July 2023

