3. SAFETY ANALYSES

3.1 ADVERSE EVENTS

3.1.1 *Available data*

Adverse events (AEs) are coded into system organ classes and preferred terms using the medical dictionary for regulatory activities (MedDRA, see section 10.3). For each AE, start and stop date(time)s are collected as well as intensity, a seriousness flag, seriousness criteria, treatment-relationship, action taken towards the study treatment and outcome.

Immediate hypersensitivity reactions (IHRs) are collected in a dedicated eCRF and are coded according to MedDRA dictionary (see section 10.3). For each IHR, start and stop date(time)s are collected as well as associated signs/symptoms, severity and suspected anaphylaxis.

3.1.2 *Derivation rules*

Pre-treatment AEs are defined as AEs starting between date of informed consent with 00:00 added as time part and the date(time) of first study treatment administration – 1 minute, extremes included.

Treatment-emergent adverse events (TEAE) are defined as AEs starting on or after first administration of any study treatment.

Adverse drug reactions (ADRs) are defined as TEAEs related to study treatment or with missing relationship.

Based on their start date(time), AEs will be allocated to the phase during which they started. Phases are defined in section 6.2.1. In case the AE start date(time) is incomplete or missing and the AE could consequently be allocated to more than one phase, a worst-case allocation will be done as detailed below:

- Treatment phase vs. non-treatment phase: AE will be allocated to the treatment phase.

A fatal AE is defined as an AE with outcome 'fatal'.

An AE for which the study treatment was discontinued is defined as an AE with action taken 'drug permanently withdrawn'.

	Statistical Analysis Plan	
CLI-10067AA1-01	Final Analysis	Final 1.0 of 30MAY2024

AE onset and duration will be calculated as follows:

- AE onset day (vs. first administration) =
 - AE start date < date of first administration: AE start date – date of first administration
 - AE start date \geq date of first administration: AE start date – date of first administration + 1 day
- AE duration (rounded as detailed in section 6.3.4) =
 - If start and stop date(time)s are available:
 - AE end date(time) – AE start date(time) + 1 minute

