Note: If AE duration is less than 1 hour, the duration will be presented in minutes. If the AE duration is 1 hour or more, but less than 1 day, it will be presented in hours. If AE duration is 1 day or more, it will be presented in days.

- If only start and stop dates are available:
 - AE end date – AE start date + 1 day
 - date of last contact – AE start date + 1 day (when the AE start date is fully known but the AE is not resolved at the end of the study); in this case the duration will be presented as “>x days”.

3.1.3 *Presentation of results*

Tables will present TEAEs and IHRs only. Pre-treatment AEs will only be listed.

An overview table will show the number and percentage of subjects with at least one event and the number of events by treatment for the following:

- TEAEs
- Serious TEAEs
- Non-serious TEAEs
- ADRs
- Serious ADRs
- Grade 3 or 4 TEAEs
- TEAEs leading to study treatment discontinuation
- TEAEs leading to death
- Immediate hypersensitivity reactions

Separate summary tables by MedDRA system organ class and preferred term will show the number and percentage of subjects with at least one event and the number of events by treatment for the aforementioned categories (except for IHRs). Each AE record in the clinical database is considered as a distinct adverse event and is counted as such. Blank system organ classes and preferred terms, if any, will be shown as ‘Not Available’ in the tables and listings.

All AEs, including pre-treatment events and all coding information will be listed. All IHR, including all reaction details will be listed. Separate listings will be prepared for the categories presented in the summary tables.

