14.3.1.6	Serious ADRs by System Organ Class and Preferred Term (Safety Set) Tabulation of the number and percentage of subjects with serious ADRs by MedDRA system organ class and preferred term. The number of events will also be shown.	SAF	AET003
14.3.1.7	Grade 3 or 4 TEAEs by System Organ Class and Preferred Term (Safety Set) Tabulation of the number and percentage of subjects with grade 3 or 4 TEAEs by MedDRA system organ class and preferred term. The number of events will also be shown.	SAF	AET003
14.3.1.8	TEAEs Leading to Study Treatment Discontinuation by System Organ Class and Preferred Term (Safety Set) Tabulation of the number and percentage of subjects with TEAEs leading to study treatment discontinuation by MedDRA system organ class and preferred term. The number of events will also be shown.	SAF	AET003
14.3.1.9	TEAEs Leading to Death by System Organ Class and Preferred Term (Safety Set) Tabulation of the number and percentage of subjects with TEAEs leading to death by MedDRA system organ class and preferred term. The number of events will also be shown.	SAF	AET003
LABORATORY DATA			
14.3.2.1	Haematology: Summary of Actual Values and Changes from Baseline (Safety Set) Descriptive statistics of haematology results and changes from baseline by treatment, parameter and analysis visit. Table sorted first by parameter, then by analysis visit. Each parameter will begin on a new page.	SAF	LBT001
14.3.2.2	Haematology: Shift from Baseline (Safety Set) [KFR] Shift table of the abnormality at each analysis visit versus the baseline abnormality per parameter. Each parameter will begin on a new page.	SAF	LBT005

	Statistical Analysis Plan		
CLI-10067AA1-01	Final Analysis	Final 1.0	of 30MAY2024

Number	Title	Analysis Set	TLFs Library Template Number
14.3.2.3	Biochemistry: Summary of Actual Values and Changes from Baseline (Safety Set) Descriptive statistics of biochemistry results and changes from baseline by treatment, parameter and analysis visit. Table sorted first by parameter, then by analysis visit. Each parameter will begin on a new page.	SAF	LBT001
14.3.2.4	Biochemistry: Shift from Baseline (Safety Set) [KFR] Shift table of the abnormality at each analysis visit versus the baseline abnormality per parameter. Each parameter will begin on a new page.	SAF	LBT005
VITAL SIGNS			

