16.2.7.9	Treatment Emergent Adverse Events Leading to Death (Randomised Set) Same as listing 16.2.7.2, but listing TEAEs leading to death only	RND	AEL002
16.2.7.10	Immediate Hypersensitivity Reactions (Randomised Set) Listing IHR along with associated signs/symptoms and suspected anaphylaxis and a reference to the related adverse event(s).	RND	AEL002
16.2.7.11	Physical Examination Abnormalities (Randomised Set) Listing of all data on abnormal physical examinations findings	RND	PEL001
LABORATORY DATA			
16.2.8.1	Laboratory Results: Haematology Full Listing (Randomised Set) Listing of all haematology results. The (non-imputed) values will be shown, as well as normal ranges, abnormality flags (L/H), clinical significance flag and fasted flag. Treatment-emergent abnormalities will be flagged.	RND	LBL001
16.2.8.2	Laboratory Results: Haematology Abnormalities (Randomised Set) Same as listing 16.2.8.1, but listing abnormal results only	RND	LBL001
16.2.8.3	Laboratory Results: Biochemistry Full Listing (Randomised Set) Same as listing 16.2.8.1, but listing biochemistry results instead	RND	LBL001
16.2.8.4	Laboratory Results: Biochemistry Abnormalities (Randomised Set) Same as listing 16.2.8.3, but listing abnormal results only	RND	LBL001
16.2.8.5	Laboratory Results: Urinalysis (Randomised Set) Listing of all urinalysis results. The (non-imputed) values will be shown, as well as normal ranges, abnormality flags (L/H/A), and clinical significance flag.	RND	LBL001
16.2.8.6	Laboratory Results: Pregnancy Test (Randomised Set) Listing of all serum and urine pregnancy results.	RND	LBL005
VITAL SIGNS			
16.2.9.1	Vital Signs: Full Listing (Randomised Set) Listing of all vital signs results, including oxygen saturation. The values will be shown, as well as changes from baseline and change abnormalities. Treatment-emergent abnormalities will be flagged.	RND	VSL002

	Statistical Analysis Plan		
CLI-10067AA1-01	Final Analysis	Final 1.0	of 30MAY2024

Number	Title	Analysis Set	TLFs Library Template Number
ECG			
16.2.10.1	Local 12-Lead ECG: Full Listing (Randomised Set)	RND	EGL001
	Listing of all triplicate/single local 12-lead ECG results and the corresponding interpretation. The values will be shown, as well as changes from baseline and abnormality categories (for QTcF). Treatment-emergent abnormalities will be flagged.		
16.2.10.2	Local 12-Lead ECG: Abnormalities (Randomised Set)	RND	EGL001

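### Immediate hypersensitivity reactions are graded outside CTCAE, their severity is not tabulated, and the SAP does not say how a severe one counts as Grade 3 or 4

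*SAP*

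**What the plan says.** **Grading.** Protocol 10.3 opens with a carve-out: "For the classification of AEs severity (except for immediate hypersensitivity reactions severity, see below". CTCAE Grades 1 to 5 apply to other adverse events, and for IHRs the reader is sent to 7.2.2.5.1. There, "The severity grade of the immediate hypersensitivity reactions should be assessed by the Investigator, considering the following grading system" introduces a three-level scale of mild, moderate and severe. Its top level is "Severe (hypoxia, hypotension, or neurological compromise".

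**Collection.** SAP 3.1.1 puts IHRs on their own eCRF page. "For each IHR, start and stop date(time)s are collected as well as associated signs/symptoms, severity and suspected anaphylaxis". For ordinary adverse events the SAP collects an intensity field. SAP 3.1 does not name the scale used in that field.

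**Tables.** SAP 3.1.3 defines the overview, Table 14.3.1.1. It has a row for Grade 3 or 4 TEAEs and a separate row for IHRs of any severity. Further tables by system organ class and preferred term give "the number of events by treatment for the aforementioned categories (except for IHRs"). The only severity table short of death is Table 14.3.1.7: "Tabulation of the number and percentage of subjects with grade 3 or 4 TEAEs by MedDRA system organ class and preferred term".

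**Listings.** SAP 3.1.3 commits to listing every IHR with all its reaction details. SAP 9.2 describes Listing 16.2.7.10 as "Listing IHR along with associated signs/symptoms and suspected anaphylaxis and a reference to the related adverse event(s").

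**The concern.** Safety and tolerability is the primary objective, and the protocol itself expects this kind of reaction with an infused antibody. A reader will look first at the Grade 3 or 4 row for serious trouble at a given dose. That row is defined on a scale from which the protocol has exempted IHRs, and the plan gives no rule connecting the two.

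A report could therefore show no Grade 3 or 4 event at a dose where a subject had a severe reaction during infusion. The IHR row would not correct the impression, because it counts skin-only urticaria and a collapse alike. The variable that separates them is collected but feeds no table.

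**Working it through.** The documents give no figure to reproduce and no expected IHR rate. The check is a trace of definitions, followed by simple arithmetic on its size.

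**1. Are the two scales interchangeable?** Compare Protocol 10.3 with 7.2.2.5.1.

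- CTCAE in 10.3 is defined by intervention needed, hospitalisation, daily activities and threat to life. It runs from 1 to 5.
- The IHR scale is defined by organ system. It has three numbered levels, with nothing corresponding to Grades 4 and 5.
- Angioedema confined to skin and subcutaneous tissue is level 1 (mild) on the IHR scale. If hospitalisation is indicated, the general definition in 10.3 makes it Grade 3.
- Oxygen saturation of 92% or less is enough for the severe IHR level. Inclusion criterion 7 admits subjects at exactly 92% at rest, so this level and a CTCAE Grade 3 need not coincide.

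The scales do not map onto each other, and neither document supplies a mapping. The wording adds to the risk: the protocol speaks of a severity grade for IHRs as well, and severe is item 3 on that list.

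**2. Does an IHR have an adverse event record?** Protocol 10.8 requires all adverse events on the AE page, with no exemption for IHRs. Listing 16.2.7.10 cross-refers to related adverse events. A linked record is therefore expected, and it is a TEAE if it starts on or after dosing (SAP 3.1.2).

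**3. What goes into that record's intensity field?** Three readings are open:

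| Reading | Intensity of the linked record | Effect on the Grade 3 or 4 result |
|---|---|---|
| A | No CTCAE grade, taking 10.3 literally | Severe IHR absent |
| B | IHR level copied across, severe read as Grade 3 | Severe IHR present, but two scales share one row |
| C | Separate CTCAE grade given to the linked event | Counted on CTCAE alone |

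Reading C is coherent, but no passage states it and it sits awkwardly with the exception in 10.3. SAP 3.1.2 has fallback rules for a missing relationship (counted as an adverse drug reaction) and for an incomplete start date (worst-case phase). It has none for a missing grade, so under A the event would drop out without notice.

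**4. Is IHR severity tabulated anywhere?** No adverse event table in SAP 9.1 (14.3.1.1 to 14.3.1.9) uses IHR severity or suspected anaphylaxis. Protocol 12.3.5.1 planned TEAEs by CTCAE grade, and such a table could have exposed ungraded events. The SAP narrows this to Grade 3 or 4, plus deaths, and SAP 7.1 does not record the change.

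**5. Size.** Protocol 12.1 gives 6 active subjects per dose, so 3 × 6 = 18 in all. For one severe IHR that is either left out or counted (exact Clopper-Pearson 95% intervals):

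| Group | Left out | Counted |
|---|---|---|
| One dose | 0/6 = 0% (0 to 45.9%) | 1/6 = 16.7% (0.4 to 64.1%) |
| All active | 0/18 = 0% (0 to 18.5%) | 1/18 = 5.6% (0.1 to 27.3%) |

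The chance of at least one severe IHR is 1 − (1 − p)^n. The rates p below are assumptions:

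| p | n = 6 | n = 18 |
|---|---|---|
| 2% | 11.4% | 30.5% |
| 5% | 26.5% | 60.3% |
| 10% | 46.9% | 85.0% |
| 20% | 73.8% | 98.2% |

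**The case against.** A reader might infer that IHRs are excluded from every severity table. The text does not say so. The exception in SAP 3.1.3 means only that the IHR category gets no table of its own by system organ class and preferred term. It removes no adverse event record from the TEAE, serious, drug reaction, Grade 3 or 4 or discontinuation tables.

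A reader might also infer that the Grade 3 or 4 result must be wrong on any reading. That is not shown either. Under reading C nothing is lost and nothing is mixed. The result is undefined rather than wrong.

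Nor is IHR severity hidden. SAP 3.1.3 promises all reaction details in the listing, and severity is one of the details collected, so the short description of Listing 16.2.7.10 does not amount to an omission. With 18 active subjects, a complete listing can be read case by case. A dangerous reaction would probably also appear elsewhere: Protocol 10.1 gives anaphylaxis as an example of a life-threatening event, so the linked record could appear among serious TEAEs or drug reactions. The Safety Advisory Committee also characterises IHRs at the end of the study. Finally, Protocol 12.3.5.1 never promised a table of IHRs by severity.

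These points stand and narrow the finding. They do not supply the missing intensity rule, and none of those other routes reports severity. A listing does not correct a summary row that reads zero.

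**Conclusion.** The point holds as a missing rule together with a severity variable that is collected but not tabulated. By protocol, an IHR is not graded on CTCAE. The SAP's severity summary short of death uses Grades 3 and 4 only, and nothing says how a severe IHR or its linked record enters that summary. It can be absent, or present on another scale.

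The size is illustrative: 16.7 percentage points in a dose group, or 5.6 points across active subjects, for each affected subject. It assumes that a severe IHR occurs and that no linked record for that subject carries Grade 3 or 4. The documents do not say that either will happen. Because the row serves the primary objective and the remedy is cheap, the SAP should be changed.

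**What to change.** 1. Add one table of IHRs by treatment, with subjects and events, split by the severity levels of Protocol 7.2.2.5.1 and by suspected anaphylaxis. Split the IHR row of Table 14.3.1.1 by severity.
2. State in SAP 3.1 that each IHR is linked to its adverse event record or records, which scale fills the intensity field of those records, and whether they count as Grade 3 or 4, including when no CTCAE grade is present. Footnote Tables 14.3.1.1 and 14.3.1.7 to match.
3. Align the description of Listing 16.2.7.10 with SAP 3.1.3. Nothing more is needed there.

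A combined row for Grade 3 or higher TEAE or severe IHR is optional. If used, it should count each subject once and be labelled as a composite of two scales.

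The cost is one small extra table and some SAP wording. No new data are needed.
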